## **6.4 Statistical Method**

### **6.4.1 Sample Size Considerations**

We based our sample size estimate on assumptions for our primary aim, as this is the most important aim for providing information to support future recommendations with regards to TXA in patients with intestinal AE. A total of 50 subjects will be enrolled with 1:1 randomization to either TXA or placebo. For the primary study endpoint of hemoglobin, we will have 80% power to detect an average increase of 25% from baseline to 3 months between TXA and placebo groups ( $\alpha = 0.05$ ). We expect 75% of patients on TXA to have a 2 gm/dl improvement in overall hemoglobin while only 25% in placebo group see a 2gm/dl improvement. We expect 75% of TXA patients to require zero blood transfusions compared to placebo group requiring 1 blood transfusion on average per patient over 3 months.

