#### 6.1.2 Method of Assignment/Randomization (if applicable)

Allocation concealment will be used to make sure the individual enrolling the trial subjects into the study has no bias towards group assignment. A statistician not directly involved in the analysis of the study will use simple randomization to create the two arms of the study (TXA vs placebo). Randomization will be carried out by using an online random number generating software, excluding the number zero. If an even number is generated, the patient will be placed in the TXA treatment arm, and if an odd number is generated the patient will be placed in the control (placebo) arm. This process will be repeated until there are 25 patients in each group.

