### **6.3.6 Removal of subjects**

- At the time of consent, participants will be informed that their participation in this research study is voluntary and they may discontinue participation without penalty at any time.
- Subjects will be withdrawn from the study by the investigator if they are to have serious adverse reactions to TXA or to protect the subjects from excessive risk due to lack of benefit demonstrated by TXA.
- Data collection prior to participant withdrawal may be retained and used in a manner that is consistent with study design and purpose unless participant expresses that their information to not used in the study

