### 7.3 Deviations/Unanticipated Problems

We will attempt to minimize missing data; however, we have planned for its occurrence. For subjects lost to follow-up, we will use all of the information available until the end of follow-up. This protocol will continue to follow subjects and perform lab tests even if a subject drops-out from the treatment portion of the study. If a subject decides that he/she does not wish to continue taking the study drug, the subject will stop the investigational treatment, but will still be strongly encouraged to continue to follow-up with the study personnel for all scheduled study follow ups (e.g., lab draws and symptom reporting), so that missing data will be minimized.

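### 6.4.1 attaches 80% power to all 50 enrolled with no allowance for loss (about 75% with 45 month-3 values and 70% with 40, if the 80% is right), and no stated analysis carries out the 7.3 promise on lost patients

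*Combined protocol and SAP*

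**What the plan says.** **Size and power.** Section 6.4.1 states: "A total of 50 subjects will be enrolled with 1:1 randomization to either TXA or placebo". For hemoglobin it adds that "we will have 80% power to detect an average increase of 25% from baseline to 3 months between TXA and placebo groups", at alpha 0.05. It gives no SD, sidedness, loss rate or evaluable number. The same paragraph holds a separate responder assumption, "We expect 75% of patients on TXA to have a 2 gm/dl improvement in overall hemoglobin", against 25% on placebo. Section 6.1.2 fixes the same total at randomization: "This process will be repeated until there are 25 patients in each group".

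**Loss.** Section 6.3.6 lets participants stop at any time and ask that data already collected not be used. It also says "Subjects will be withdrawn from the study by the investigator" for serious adverse reactions to TXA or "to protect the subjects from excessive risk due to lack of benefit demonstrated by TXA". Section 7.3 says "We will attempt to minimize missing data; however, we have planned for its occurrence" and "For subjects lost to follow-up, we will use all of the information available until the end of follow-up". It continues lab tests in patients who stop the study drug.

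**Analysis.** Section 6.4.2 plans baseline-adjusted linear regression of absolute and percent change in hemoglobin and names no visit. The baseline-to-3-months endpoint comes from 6.4.1. Section 6.4.3 says only that missing data will be noted and discussed. Section 5.1 schedules blood counts at baseline and months 1, 2 and 3.

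**The concern.** The power statement and the handling of loss do not fit together. The 80% is attached to the number enrolled, and randomization stops at that number, so every missing month-3 count lowers power from whatever it really is.

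Section 7.3 says that missing data have been planned for, but nothing in 6.4 supplies the plan. A regression with one month-3 change per patient leaves out anyone without a month-3 count, so that patient's month 1 and 2 counts go unused.

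Two things are at stake: a moderate loss of power, and some bias if the patients who leave are those doing badly. Section 7.3 reduces the first by following patients off drug, but it does not say whether this covers patients withdrawn under 6.3.6, and it cannot reach those lost to follow-up.

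**Working it through.** **1. Inputs.** From 6.4.1 and 6.1.2: 25 per arm, alpha 0.05, power 80%, effect 25%. Assumed: a two-sided test (one-sided also shown); the effect read as a 25-point difference between arms in percent change; loss of 10% (45 values) or 20% (40 values).

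**2. The plan's own figure.** Without an SD the 80% can be neither reproduced nor refuted. It can be turned round to find the standardized difference d that it implies.
- Normal approximation: d = (1.960 + 0.842) × √(2/25) = 0.792.
- Noncentral t, with n1 + n2 − 2 degrees of freedom and noncentrality δ = d / √(1/n1 + 1/n2): 80% at 25 + 25 needs d = 0.8087, so SD = 25 / 0.8087 = 30.9 points.
- One-sided: d = 0.7134, SD = 25 / 0.7134 = 35.0 points.

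**3. Power with fewer month-3 values, d held at 0.8087.**

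| Values per arm | δ | Two-sided power |
|---|---|---|
| 25 + 25 | 2.859 | 80.0% |
| 24 + 24 | 2.801 | 78.3% |
| 23 + 22 | 2.712 | 75.5% |
| 25 + 20 | 2.696 | 75.0% |
| 20 + 20 | 2.557 | 70.3% |
| 25 + 15 | 2.476 | 67.5% |

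Spending one degree of freedom on baseline changes these by less than 0.1 point. One-sided power at 48, 45 and 40 is 78.5%, 76.1% and 71.6%. The two-sided normal approximation gives 75.7% at 45 and 70.7% at 40.

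**4. Dependence on the missing SD (assumed values, 25-point effect, two-sided).**

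| SD | 50 | 45 | 40 |
|---|---|---|---|
| 25 | 93.4% | 90.6% | 86.9% |
| 30 | 82.3% | 78.0% | 72.8% |
| 35 | 69.7% | 64.9% | 59.5% |
| 40 | 58.1% | 53.6% | 48.7% |

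**5. Responder comparison.** For 75% v 25%, Fisher's exact test has power 94.5%, 92.5% and 83.4% at 50, 45 and 40. The point concerns the mean comparison only.

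**6. Loss that follows low hemoglobin.** Simulation with 25 per arm, loss after month 1 or 2, and assumed baseline-adjusted correlation between visits of 0.3, 0.5 or 0.7. Bias is in points out of 25.
- Loss partly dependent on the last count: the month-3-only estimate is low by about 0.3 to 1.2 at 10% loss, and by 0.8 to 1.8 at 20%.
- Extreme case, in which the patients with the lowest last count are always the ones lost: low by about 1 to 3 at 10% loss, with about 3.3 placebo and 1.7 TXA patients lost on average. A variant with the full effect present from month 1 gave 2.3 to 4.8, so the size depends on the assumed course.
- A repeated-measures model using all visits kept the bias within about 0.3 in the partly dependent settings and in the extreme case (the month-1 variant apart).

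**7. Power gain from using all visits, random loss, correlation 0.3 / 0.5 / 0.7.**
- 10% loss: 74.1 / 74.2 / 74.6% rises to 74.5 / 75.5 / 77.2%, a gain of 0.4 / 1.3 / 2.6 points.
- 20% loss: 69.5 / 68.6 / 69.5% rises to 70.5 / 71.5 / 74.7%, a gain of 1.0 / 2.9 / 5.2 points.

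The simulated month-3-only figures lie up to about 2 points below step 3, so read the differences rather than the levels. Type I error at 20% loss and correlation 0.7 was 0.048 to 0.054 for month 3 only and 0.046 to 0.053 for all visits.

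**The case against.** **The SD matters more than loss.** This stands. In step 4, power at 50 runs from 58% to 93% across the assumed SDs, against a drop of 5 to 10 points from loss. A reader might infer that 6.4.1 contains an arithmetic error, or that power must fall below 80% once anyone is lost. Neither follows: with an SD of 25, power at 40 values is still 87%.

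**The regression could use lost patients' counts.** This also stands. A reader might infer that the planned regression is unable to honor 7.3. But 6.4.2 names no visit, and a last-value rule or imputation would work within linear regression. The supportable statement is that no such method is given.

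**Loss may be small.** The trial is short and has one site, requires stated willingness to comply, excludes patients unable to keep to treatment for 3 months, and follows patients off drug. The documents give no loss rate, so 10% and 20% are illustrations, not forecasts. The 80% cut-off in 7.6 also equals 40 patients, but it concerns recruitment, not loss after randomization.

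**The direction of bias is not settled.** More placebo than TXA loss follows if the lack-of-benefit ground is read as the patient's own lack of benefit, and the wording is open. The other ground, serious reactions to TXA, could remove TXA patients; it was not modelled and could act differently.

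None of this supplies the missing allowance, or a method for what 7.3 promises.

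**Conclusion.** The point holds as a moderate, inexpensive improvement that should be made. Section 6.4.1 ties 80% power to 50 enrolled with no allowance for loss that the protocol itself foresees. If the 80% is right for 50 month-3 values, the chance of missing the stated mean effect rises from 20% to about 25% with 45 values and about 30% with 40. This rests on the assumed loss rates, a two-sided test and roughly balanced loss.

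The bias figures rest on assumed correlations, an assumed course of the effect and loss driven by low hemoglobin; the partly dependent range is the one to quote first. The documents do not show that the trial is underpowered, that such loss will occur, or that N must rise.

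**What to change.** Keep N at 50 and change three sections.

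1. **6.4.1:** State that the 80% applies to 50 patients with a month-3 hemoglobin (25 per arm). Give the SD and sidedness used. Add that, if the 80% is right, a month-3-only comparison has about 75% power with 45 evaluable and 70% with 40, and that the model in item 2 is expected to do equally well or slightly better.
2. **6.4.2:** Make the primary analysis a repeated-measures model of one named hemoglobin measure (absolute or percent change, for the sponsor to choose) at months 1, 2 and 3, adjusted for baseline, with the month-3 arm contrast primary. Include every randomized patient with at least one post-baseline count, except those who ask under 6.3.6 that their data not be used.
3. **6.4.3:** Refer to this model, and report loss by arm and reason, including patients with no post-baseline count, whom the model cannot include.

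**Cost.** No added patients or visits, since 5.1 already schedules the counts. The stated power becomes less favorable. The model is slightly more complex and assumes that loss depends only on observed values. The power gain is small: about 0.4 to 3 points at 10% random loss and 1 to 5 at 20%, depending on the assumed correlation. The main return is a stated method for 7.3 and less bias if low hemoglobin drives loss.

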### **6.4.2 Planned Analyses**

We will characterize subjects with regard to baseline and follow up hemoglobin/hematocrit (H/H) and other endpoints previously described. We will summarize demographics and other predictors of clinical status. Continuous variables will be summarized by mean, standard deviation and range as appropriate. The primary analysis will compare the absolute and percent change in hemoglobin with adjustment for baseline in linear regression models. Using multivariable logistic regression models adjusting for baseline hemoglobin, we will assess if the odds of achieving a clinically relevant improvement in hemoglobin differs by treatment assignment. The secondary outcomes will be analyzed similarly using linear regression models adjusting for baseline values.

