## **2.2 Prior clinical experience**

The principal investigator for this study has been using TXA in his clinic as an off-label drug for the treatment of small bowel AEs. Those who were treated with TXA were those patients that have failed standard therapy. Failure of standard therapy is defined as continued GI bleeding and need for blood transfusions despite endoscopic ablation, octreotide therapy and iron supplementation for at least 3-6 months. Thus far, 9 patients have been treated with TXA therapy consisting of 650 mg oral tablets taken three times per day for 3 months. In 8 of those patients there was an observed clinical response defined as stabilization of hemoglobin which was not previously achieved with prior therapy. Although this sample size of patients was not a controlled study accounting for confounding variables, it does strongly highlight the potential beneficial therapeutic effects of TXA. Of note, there were no side effects observed by the 9 patients.

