### **3.3.2 Potential Benefits**

If TXA is shown to decrease the need for further blood transfusions and hospital admissions, it becomes a viable option for patients affected by intestinal AEs. Specifically, for patients who experience recurrent blood loss despite current standard medical therapy.

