### 4.2 Primary Objective

To determine whether oral therapy with TXA results in improvement in serum hemoglobin concentration and/or requirement for PRBC transfusion compared to placebo in patients treated with standard endoscopic ablation and iron supplementation

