### 5.2 Outcome Variables

#### 5.2.1 Primary Outcome Variables

Primary outcome variables include hemoglobin concentration and the requirement of packed RBC transfusion.

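### Section 6.4.2 gives no between-arm analysis for transfusion, a listed primary outcome; no rule for judging the and/or objective; and a hemoglobin responder definition that ignores transfusion

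*Combined protocol and SAP*

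**What the plan says.** **Outcomes and objective.** Section 5.2.1 (repeated in the synopsis) states: "Primary outcome variables include hemoglobin concentration and the requirement of packed RBC transfusion". Section 4.2 asks about "improvement in serum hemoglobin concentration and/or requirement for PRBC transfusion compared to placebo". Section 3.3.2 ties the hoped-for benefit to transfusion: "If TXA is shown to decrease the need for further blood transfusions and hospital admissions, it becomes a viable option".

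**Analysis.** Section 6.4.2 states: "The primary analysis will compare the absolute and percent change in hemoglobin with adjustment for baseline in linear regression models". It adds a logistic model adjusted for baseline hemoglobin, in which "we will assess if the odds of achieving a clinically relevant improvement in hemoglobin differs by treatment assignment". Its last sentence assigns linear regression with baseline adjustment to the secondary outcomes. Section 5.2.2 lists those as hospitalizations, endoscopic interventions and side effects; transfusion is not among them. The only other text in 6.4.2 that could reach transfusion promises to characterize subjects on the endpoints, which is descriptive.

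**Sample size.** Section 6.4.1 refers to hemoglobin, in the singular, as the study's primary endpoint and gives 80% power for it alone. It then adds: "We expect 75% of TXA patients to require zero blood transfusions compared to placebo group requiring 1 blood transfusion on average".

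**Post-baseline events.** Blood counts are taken at months 1, 2 and 3 (section 5.1). Section 6.4.3 covers missing data. Section 7.3 covers drop-out and stopping study drug, and says: "For subjects lost to follow-up, we will use all of the information available until the end of follow-up". Neither mentions a hemoglobin value measured after a transfusion.

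**A conflicting label.** One exclusion criterion in section 5.3.2 removes patients who refuse blood products, on the ground that a secondary outcome would be fixed in advance. That appears to call transfusion secondary.

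**The concern.** Three gaps meet in one section.

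1. A listed primary outcome has no named between-arm analysis. Whether it is primary or secondary depends on which section one reads.
2. The and/or objective has no decision rule. It could mean that either outcome suffices, that both are needed, or that hemoglobin leads. Each reading has a different error rate and power. Hemoglobin itself is to be compared on two scales, with neither named as decisive.
3. The responder analysis takes hemoglobin as measured. A patient whose count rises because of transfused blood is then scored as improved, in a trial whose other primary outcome is avoiding transfusion. The plan itself expects transfusion to be unequal between arms, so this misclassification need not cancel out.

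At stake is whether a reader of the results can tell what was tested, at what error rate, and what a hemoglobin responder means.

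**Working it through.** **The plan's own power figure.** It cannot be reproduced, because no standard deviation is given. Solving backwards for 25 per arm, two-sided alpha 0.05 and 80% power: SD = 25 / [(1.960 + 0.842) × √(2/25)] = 31.5 percentage points. The other reading of the effect, 75% against 25% of patients gaining 2 g/dL, has 94.5% power by exact Fisher test, so it is not the source of the 80%.

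**Expected transfusion by arm.** Inputs from 6.4.1 are a placebo mean of 1 and 75% of TXA patients with none. The count distribution is my assumption.
- Placebo total: 25 × 1 = 25 transfusions.
- Placebo patients transfused, Poisson: 25 × (1 − e⁻¹) = 15.8. Negative binomial with dispersion 2: 25 × (1 − 3^(−1/2)) = 10.6.
- TXA patients transfused: 25 × 0.25 = 6.25.
- TXA mean, Poisson: −ln(0.75) = 0.288. Dispersion 2: (0.75⁻² − 1)/2 = 0.389.

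**Shift in the measured mean difference.** Let k be the hemoglobin still retained per transfusion at month 3 (assumed 0.5 or 1.0 g/dL). The shift is (placebo mean − TXA mean) × k.
- Poisson: (1 − 0.288) × 0.5 = 0.36 g/dL; × 1.0 = 0.71 g/dL.
- Dispersion 2: (1 − 0.389) × 0.5 = 0.31 g/dL; × 1.0 = 0.61 g/dL.

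**Responder comparison: direction.** In this illustration, hemoglobin change without transfusion is normal with SD 1.483, matched to 75% against 25% responders. Counts are Poisson and are linked to hemoglobin in three ways. Entries are exact Fisher power at 25 per arm; with no transfusion effect it is 94.5%.

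| Who is transfused | As measured, k = 0.5 | As measured, k = 1.0 | Transfusion-free responder |
|---|---|---|---|
| At random | 79% | 52% | 94% |
| Moderately tied to low hemoglobin (correlation −0.5) | 87% | 60% | 91% |
| Strictly the lowest hemoglobin | 99% | 98% | 94% |

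The as-measured responder analysis can lose or gain power. In the last row the transfusion-free definition is the weaker of the two.

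**Error rate of and/or.** If either outcome suffices, each at 0.05, and the tests are independent: 1 − 0.95² = 9.75%. For two normal tests with correlation 0.3, 0.5 or 0.9 it is 9.5%, 9.1% or 7.0%. If both must succeed there is no inflation.

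**Power of a transfusion-free test.** Fisher exact, 75% on TXA against an assumed placebo transfusion-free rate. The placebo rates come from a mean of 1 with Poisson counts, then negative binomial counts with dispersion 0.5, 1 and 2.

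| Placebo transfusion-free | Power at 0.05 | Power at 0.025 |
|---|---|---|
| 36.8% | 74% | 63% |
| 44.4% | 52% | 40% |
| 50.0% | 36% | 25% |
| 57.7% | 17% | 11% |

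**The case against.** **Hemoglobin is already the lead test.** Section 6.4.1 names it as the primary endpoint and powers only it, and 6.4.2 describes the primary analysis in hemoglobin terms. This stands in part. A reader might infer from and/or that the trial will run at 9.75% error, or that success will be defined after the data are seen. The documents do not go that far: no section says that either outcome alone suffices at 0.05. Equally, none sets an order or divides alpha.

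**Transfusion is covered as a secondary outcome.** If the exclusion criterion's label is taken at face value, the last sentence of 6.4.2 applies. Part of the problem is then a labelling conflict, which is fair. It does not close the gap: sections 4.2 and 5.2.1 say otherwise, and a linear model adjusted for baseline has no defined baseline for on-study transfusions.

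**As-measured hemoglobin is a legitimate comparison.** It is, and it should stay primary. A reader might take the 0.36 to 0.71 g/dL shift as a bias that the fix removes. It is neither. It is the difference between two estimands, it remains after the fix, and it vanishes as a departure from plan if the expectations in 6.4.1 already include transfusion.

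**Transfusion is treated as failure elsewhere.** Section 2.2 says "Failure of standard therapy is defined as continued GI bleeding and need for blood transfusions despite endoscopic ablation". A reader might see a contradiction with 6.4.2. But that sentence describes which patients received off-label TXA before this trial, and the stabilization criterion in the same section describes their response. Neither defines a trial endpoint. Sections 4.1 and 6.4.1 both give 2 g/dL, so the threshold missing from 6.4.2 is largely a cross-reference.

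**Conclusion.** The concern holds as a should-fix point. Three textual facts need no assumption: transfusion is listed as primary without a named between-arm analysis, and is apparently labelled secondary elsewhere; the and/or objective has no decision rule; and the responder analysis has no rule for transfused patients.

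The sizes are conditional. The 9.75% is an upper figure for independent tests under one unstated reading. The 0.36 to 0.71 g/dL needs Poisson counts, 0.5 to 1.0 g/dL retained per transfusion, and expectations in 6.4.1 that exclude transfusion. It is tempting to conclude that the plan is biased against TXA or underpowered because of transfusion. The documents do not support that. They give no SD, no baseline hemoglobin and no gain per transfusion, and the responder illustration moves in both directions.

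**What to change.** Change the analysis text in 6.4.2, plus one label elsewhere. Patient care does not change.

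1. Define hemoglobin response as a rise of at least 2 g/dL (the figure in 4.1 and 6.4.1) at 3 months with no red cell transfusion since randomization. Report the two components separately, so that a transfusion difference is not read as a hemoglobin effect.
2. Keep as-measured hemoglobin change as the primary analysis and state that it estimates the effect regardless of transfusion. Name one scale, absolute or percent, as decisive. Add one sensitivity analysis that ranks transfused patients below all others.
3. Name one transfusion analysis: transfusion-free, yes or no, compared by arm (for example by Fisher's exact test), in place of a linear model with an undefined baseline.
4. State the and/or rule. Either test hemoglobin first and transfusion second in fixed order, which fits 6.4.1, or use Holm's procedure if either result alone is to count.
5. Reconcile the blood-refusal exclusion criterion with the synopsis and sections 4.2 and 5.2.1.

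**Cost.** Wording, and a date for each transfusion; need for transfusion is already monitored under 5.1. The responder becomes a composite. No section states a transfusion trigger, so the composite partly reflects local practice, and it can have less power if only the patients with the lowest hemoglobin are transfused (94% against 98 to 99% in the illustration). The transfusion-free test has 17 to 74% power depending on the placebo rate. Fixed order costs the hemoglobin test nothing. Under Holm, a hemoglobin test held to 0.025 would have about 71% power instead of 80% at the SD implied by the plan; that is the worst case, since Holm restores 0.05 when the transfusion test succeeds.

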## 4 - Study Objectives

### 4.1 Hypothesis

We expect 75% of patients on TXA to have a 2 gm/dl improvement in overall hemoglobin while only 25% in placebo group see a 2gm/dl improvement. We expect 75% of TXA patients to require zero blood transfusions compared to placebo group requiring 1 blood transfusion on average per patient over 3 months.

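### Absolute and percent change in hemoglobin are both the primary analysis, unranked and unadjusted, while the power statement uses a 25% average increase and the hypothesis a 2 g/dL responder rate: there is no single primary hemoglobin result

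*Combined protocol and SAP*

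**What the plan says.** Section 5.2.1 gives the outcome without a scale, summary measure or time point: "Primary outcome variables include hemoglobin concentration and the requirement of packed RBC transfusion".

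Section 6.4.2 then sets the analysis: "The primary analysis will compare the absolute and percent change in hemoglobin with adjustment for baseline in linear regression models". The next sentence adds a logistic model, adjusted for baseline hemoglobin, in which "we will assess if the odds of achieving a clinically relevant improvement in hemoglobin differs by treatment assignment". It gives no threshold for that improvement and does not say where the model ranks.

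Section 6.4.1 claims "80% power to detect an average increase of 25% from baseline to 3 months between TXA and placebo groups". The same section goes on: "We expect 75% of patients on TXA to have a 2 gm/dl improvement in overall hemoglobin while only 25% in placebo group" are expected to do so. Section 4.1 makes that responder statement the study hypothesis.

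No section ranks these analyses, says how they combine, or adjusts for more than one test. The plan states no baseline hemoglobin and no SD of change, and eligibility (5.3.2) asks for symptomatic anemia without a hemoglobin limit.

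**The concern.** Absolute and percent change are different response variables. Percent change divides each patient's gain by that patient's baseline, so the same gain in g/dL counts for more in a patient who starts low. The two can therefore fall on opposite sides of p = 0.05 in the same data. With both labelled primary, the team could headline whichever is favourable, and a reader could not tell whether that choice preceded the data.

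The surrounding sections do not settle the matter. The power statement points to percent change. The hypothesis points to a patient-level threshold in g/dL. The outcome list points to neither. At stake are the meaning of a positive hemoglobin result and some excess false-positive risk.

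**Working it through.** **1. The plan's own power figure.** Inputs from 6.4.1: 50 subjects at 1:1, so 25 per arm; alpha 0.05 (two-sided assumed, as the section does not say); 80% power; a 25% average increase. Without an SD the 80% cannot be reproduced, only solved backwards.

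- Normal approximation: d = (1.960 + 0.842)/√(25/2) = 2.802/3.536 = 0.79.
- Noncentral t, 48 degrees of freedom: d = 0.81 (0.8087).
- Implied SD of percent change: 25/0.8087 = 31 percentage points, a figure the plan never states.
- For a mean difference of 2 g/dL the same d would need an SD of 2/0.8087 = 2.47 g/dL.

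**2. Whether the 80% comes from the responder statement.** Inputs: 75% versus 25%, 25 per arm, two-sided 0.05.

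- Power = Φ[(0.5 × √25 − 1.960 × √0.5)/√0.375] = Φ[(2.5 − 1.386)/0.612] = Φ(1.82) = 96.6%. Fisher's exact test gives 94.5%.
- Size for 80% power: n = (1.386 + 0.842 × 0.612)²/0.5² = 14.5, so 15 per arm (19 with continuity correction).

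So the 80% does not come from the responder statement, and section 6.4.1 holds two design targets that do not correspond.

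**3. How the two targets relate.** A 25% rise is 0.25 × baseline: 1.5 g/dL at a baseline of 6, 2.0 at 8 and 2.5 at 10. A 2 g/dL rise is 33% at 6, 25% at 8 and 20% at 10. These baselines are illustrative. The targets are also different kinds of quantity. The 25% is a difference between group averages; the 2 g/dL is a threshold for single patients. With normal changes of equal SD, 75% versus 25% above a common threshold puts the means 2 × 0.6745 = 1.35 SD apart. At the 0.81 SD that 80% power implies, with arm means symmetric about 2 g/dL, the split would be Φ(0.405) = 66% versus 34%.

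**4. Cost of leaving both scales primary.** Simulation, all values assumed: 25 per arm; baseline mean 8.5 g/dL, SD 1.2 or 2.0, with values below 5 set to 5; change = 0.5 − 0.4 × (baseline − 8.5) + effect × treatment + error with SD 1.5 g/dL; linear regression on treatment and baseline; 20,000 runs per row.

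| True effect (g/dL) | Baseline SD | Absolute p<0.05 | Percent p<0.05 | Either | The two disagree |
|---|---|---|---|---|---|
| 0 | 1.2 | 5.2% | 5.2% | 6.0% | 1.6% |
| 0 | 2.0 | 4.9% | 4.9% | 6.0% | 2.2% |
| 1.2 | 1.2 | 78.4% | 77.2% | 79.8% | 3.9% |
| 1.2 | 2.0 | 78.5% | 74.2% | 80.4% | 8.0% |

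Across further scenarios with change SD between 1.5 and 2 g/dL, the null rate for either scale ran from about 5.5% to 7%.

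**5. If the responder test may also carry the claim.** Adding an unadjusted test of a rise of at least 2 g/dL gave 10.0% and 9.75% in the two null rows above, and about 9 to 11% over the wider scenarios. Using a logistic responder model instead, in separate runs of 6,000 per scenario, gave 8.5 to 9.5%.

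**The case against.** The strongest reply is that the plan is less loose than it looks. Only two quantities are called primary, both come from the same measurements, both models adjust for baseline, and the two tests are highly correlated. Most of this stands, and it rules out several stronger readings that a reader might infer.

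- *Four competing definitions of the endpoint.* Only absolute and percent change carry the primary label. The 25% is the effect used for power, the 2 g/dL rate is an expectation, and the logistic model is not called primary.
- *The targets agree only at a baseline of 8 g/dL.* The numbers match in size at 2/0.25 = 8, but a group mean difference and a patient-level threshold need not agree even there.
- *Two tests at 5% give nearly 10% false positives.* Independent tests would give 1 − 0.95² = 9.75%. These are far from independent, and the simulated rate is 5.5 to 7%.
- *The trial would have one primary result once the scale is fixed.* Section 4.2 asks about "improvement in serum hemoglobin concentration and/or requirement for PRBC transfusion compared to placebo", so transfusion would remain a second primary outcome.

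Baseline adjustment reduces the difference between the scales but does not remove it: every simulation above adjusted for baseline, and disagreement remained. One could also argue for keeping percent change, since it is the scale of the power statement. Naming it alone would equally end the ambiguity. Absolute change is preferred here because the hypothesis is in g/dL and hemoglobin concentration is the listed outcome. That is a judgement, not a correction of an error.

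**Conclusion.** The point holds in limited form. Section 6.4.2 names two primary hemoglobin analyses without rank or adjustment, and neither the power statement nor the hypothesis resolves the choice. That conclusion rests on the text alone.

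The size is modest and rests on assumed baselines and SDs: a false-positive rate of about 5.5 to 7% instead of 5% for either change scale, about 9 to 11% only if the responder test is also allowed to decide, and disagreement between the scales in about 4 to 8% of trials at a true effect of 1.2 g/dL. The main harm is the open choice of which result to headline, more than the error rate. The plan should be changed, but the defect does not undermine the trial's design.

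**What to change.** - **Sections 5.2.1 and 6.4.2:** name one primary hemoglobin variable, the absolute change in g/dL from baseline to month 3, compared between arms by linear regression adjusted for baseline. State that percent change is descriptive.
- **Section 6.4.2:** define the improvement in the logistic model as a rise of at least 2 g/dL at month 3, the protocol's own figure, and label that analysis supportive.
- **Section 6.4.1:** restate the detectable difference for 25 per arm in g/dL, with its assumed SD and the source of that SD. At 80% power and two-sided 0.05 it is about 0.81 × SD. For illustration, an SD of 1.5 gives 0.81 × 1.5 = 1.2 g/dL and an SD of 2 gives 0.81 × 2 = 1.6 g/dL.

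Cost: no new data or visits, since blood counts at baseline and month 3 are already scheduled. Percent change can no longer carry the primary claim. The change is also more than wording, because the power statement must be redone with an explicit SD that the plan now lacks. The rank of transfusion as the other primary outcome needs its own decision.
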